## **5.6.2 Clinical Laboratory Evaluation**

Clinical laboratory values (haematology, biochemistry, including eGFR and coagulation, urinalysis) are collected at V1a, V2, V3, EDV (if EDV performed before V3) and, if applicable, UNS for each laboratory parameter. Thyroid function will be assessed at V1a.

A serum pregnancy test at V1a and urine pregnancy tests at V1a, V2, V3, EDV (if EDV performed before V3) and, if applicable, UNS will be performed for all females of childbearing potential.

The following parameters are collected:

**Haematology:** Haemoglobin, haematocrit, red blood cell (RBC) count, white blood cell (WBC) count, differential - neutrophils, eosinophils, lymphocytes, monocytes and basophils, and platelet count.

**Biochemistry:** Sodium, potassium, chloride, calcium, phosphate, blood urea nitrogen, aspartate transaminase (AST), alanine transaminase (ALT), gamma-glutamyl transferase (GGT), lactate dehydrogenase (LDH), alkaline phosphatase, creatine phosphokinase (CPK), creatinine, glucose, C-reactive protein, albumin, total protein, total cholesterol, low-density lipoprotein-cholesterol, high-density lipoprotein-cholesterol, triglycerides, and total bilirubin (bilirubin will be fractionated direct/indirect if elevated).

Sodium levels will be monitored for signs of **hyponatraemia**. Patients will be classified by their minimum post-baseline sodium level according to the following categories:

$\geq 135$  mEq/L

130 -  $< 135$  mEq/L

125 -  $< 130$  mEq/L

$< 125$  mEq/L

and for any decrease from baseline  $> 10$  mEq/L.

**eGFR** will be estimated based on serum creatinine value (see CTP 11.4.3).

**Coagulation:** INR and activated partial thromboplastin time (aPTT).

**Thyroid function (at V1a only):** total triiodothyronine, free triiodothyronine, total thyroxine, free thyroxine, thyroid stimulating hormone.

**Serum pregnancy test (at V1a only):**  $\beta$ -hCG in females of childbearing potential.

**Urinalysis:**

- local: pH, specific gravity, protein, blood, glucose, ketones, bilirubin, urobilinogen, leukocytes, nitrite (local dipstick). Microscopy and other appropriate tests (as needed) will be performed if dipstick indicates any significant abnormality.
- central: U-Casts, U-Crystals, U-Epithelials, U-Erythrocytes quan., U-Leucocytes quan., U-Others.

**Urine pregnancy tests:** in females of childbearing potential.

All laboratory values will be classified as normal or abnormal according to the laboratories' normal ranges and as clinically significant (yes/no) according to the assessment of the investigator.

The following statistical outputs will be provided:

[Table 15.3.2.1.1 Summary of Clinical Laboratory Tests: Haematology – Safety Set](#)

[Table 15.3.2.1.2 Summary of Clinical Laboratory Tests: Biochemistry – Safety Set](#)

[Table 15.3.2.1.3 Summary of Clinical Laboratory Tests: Coagulation – Safety Set](#)

The default summary statistics of clinical laboratory test results for haematology, biochemistry (including eGRF) and coagulation will be presented by treatment group and in total by visit slots (if applicable) at V1, baseline, V3, EDV (if applicable) and Endpoint. The absolute change from baseline will be presented as well.

[Table 15.3.2.2.1 Clinical Laboratory Tests: Incidence of Haematology Abnormalities – Safety Set](#)

[Table 15.3.2.2.2 Clinical Laboratory Tests: Incidence of Biochemistry Abnormalities – Safety Set](#)

[Table 15.3.2.2.3 Clinical Laboratory Tests: Incidence of Coagulation Abnormalities – Safety Set](#)

The number and percentage of patients with Low, CS Low, Normal, High, and CS High categories of each laboratory parameter will be displayed by treatment group and in total. Percentages will be based on the number of patients at the specified visit slot.

[Table 15.3.2.3.1 Clinical Laboratory Tests: Shift Table of Haematology Results from Baseline to Endpoint – Safety Set](#)

[Table 15.3.2.3.2 Clinical Laboratory Tests: Shift Table of Biochemistry Results to Endpoint – Safety Set](#)

[Table 15.3.2.3.3 Clinical Laboratory Tests: Shift Table of Coagulation Results to Endpoint – Safety Set](#)

Shift tables showing changes in the number and frequency of patients with respect to the normal range and clinical significance between baseline and endpoint by treatment will be provided. Patients with missing data will be presented as part of a “missing” category.

[Table 15.3.2.4.1 Clinical Laboratory Tests: Shift Table of Haematology Results from Baseline to Worst Post Baseline Value – Safety Set](#)

[Table 15.3.2.4.2 Clinical Laboratory Tests: Shift Table of Biochemistry Results from Baseline to Worst Post Baseline Value – Safety Set](#)

[Table 15.3.2.4.3 Clinical Laboratory Tests: Shift Table of Coagulation Results from Baseline to Worst Post Baseline Value – Safety Set](#)

Shift tables showing changes in the number and frequency of patients with respect to the normal range and clinical significance between baseline and the worst-post-baseline-value by treatment will be provided. Patients with missing data will be presented as part of a “missing” category.

[Table 15.3.2.5.1 Clinical Laboratory Tests: Incidence Clinically Significant Urinalysis Results \(Local Dipstick\) – Safety Set](#)

Clinically significant values of urinalysis parameters (collected using local dipstick) will be summarised by visit using default frequency tabulation by treatment group and in total. The number of patients with any CS abnormalities will be summarised. Visit Slots will be used.

[Table 15.3.2.5.2 Clinical Laboratory Tests: Incidence of Urinalysis Results \(Central Laboratory\) – Safety Set](#)

Clinically significant values of urinalysis parameters (provided by central laboratory) will be summarised by visit using default frequency tabulation by treatment group and in total. The number of patients with any CS abnormalities will be summarised. Visit Slots will be used.

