## 2.5 Treatments

Treatment name	Dosage Form	Active ingredient	Strength/concentration
ESL	Tablet	Eslicarbazepine acetate (ESL)	800 mg
Placebo	Tablet	None	Not applicable

Treatment with IMP will start at V1b (i.e. within 120 hours after primary stroke, or since last time seen well) and will be continued for 30 days. Thereafter, the IMP will be tapered off, as applicable. The dosing will be as follows:

Patients with an eGFR  $> 60$  mL/min/1.73 m^2 will take one tablet once daily (800 mg ESL or placebo). Patients with moderate renal impairment at V1a, defined as eGFR 30 – 60 mL/min/1.73 m^2, will take half a tablet once daily (400 mg ESL or placebo). As soon as eGFR has improved to  $> 60$  mL/min/1.73 m^2, the dose will be increased to one tablet once daily (800 mg ESL or placebo). Patients developing moderate renal impairment during IMP intake should be adjusted to 400 mg, if applicable. Worsening of renal function with an eGFR  $< 30$  mL/min/1.73 m^2 must lead to discontinuation of IMP intake (dose independent) without down-titration.

Patients taking one tablet once daily (800 mg ESL or placebo) must be down-titrated for 7 days before stopping intake of IMP i.e. those patients will take half a tablet (400 mg ESL or placebo) from Day 31 to Day 37. Patients taking half a tablet once daily (400 mg ESL or placebo) on Day 30 do not require down-titration i.e. they will take the last IMP on Day 30.

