**Table 3: Visit Slotting**

Visit Slot/ Label	Target Day	Description
V1a	-	Screening/baseline, within 120 hours after stroke, or since last time seen well
V1b	1	Day 1, within 120 hours after stroke, or since last time seen well
V2	8	Closest non missing assessment to target day between study day 2 and 31
V3	38	Closest non missing assessment to target day between study day 32 and 71
V4	85	Closest non missing assessment to target day between study day 72 and 171
V5	183	Closest non missing assessment to target day between study day 172 and 242
V6	267	Closest non missing assessment to target day between study day 243 and 353
V7	365	Closest non missing assessment to target day between study day 354 and 437
V8	449	Closest non missing assessment to target day between study day 438 and 533
EOT	547	Closest non missing assessment to target day between study day 534 and >547

EDV	EDV	Early discontinuation visit
-----	-----	-----------------------------

If, for any variable, a visit was not scheduled (e.g. V4 for vital signs), the respective measurement will be assigned to the visit slot with the closest target day where a visit was scheduled. If two measurements fall into that slot, the closest one to target day will be used.

If, for any safety variable, V1b is not scheduled and a measurement is taken on Study Day 1, this measurement will be slotted to V2 if the assessment was done after first IMP intake.

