## **Endpoint value**

The endpoint value for an efficacy variable is defined as the last non-missing value collected after first intake of IMP before or at the respective endpoint (within the time window of interest i.e. 6 month-period, 12 month-period and 18 month-period).

The endpoint for a safety variable is defined as the last non-missing value collected after first intake of IMP that is no baseline value.

**Absolute change from baseline** will be calculated as

$$\text{Absolute Change from Baseline at Visit } X = \text{Value at Visit } X - \text{Baseline Value}$$

**Relative change from baseline (%)** will be calculated as

$$\text{Relative Change from Baseline at Visit } X = \frac{\text{Value at Visit } X - \text{Baseline Value}}{\text{Baseline Value}} \times 100$$

Note: Patients with a baseline value of '0' will be excluded from the calculation of relative change.

See section 5.4.1 for the definition of first and last IMP intakes.

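### Laboratory summary tables omit V2, so no scheduled visit during full dosing is listed for mean values or mean changes

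*SAP*

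**What the plan says.** **Collection.** SAP section 5.6.2 states: "Clinical laboratory values (haematology, biochemistry, including eGFR and coagulation, urinalysis) are collected at V1a, V2, V3". An EDV held before V3 and unscheduled visits are added to these. The schedules in the protocol and in SAP section 1 agree, and neither has a blood sample at V1b.

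**Presentation.** For Tables 15.3.2.1.1 to 15.3.2.1.3, the same section gives the default summary statistics "by visit slots (if applicable) at V1, baseline, V3, EDV (if applicable) and Endpoint", and continues: "The absolute change from baseline will be presented as well". No separate visit list is given for the change, so it follows the same list.

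**Dosing.** Under SAP section 2.5 treatment runs for 30 days. Patients on half a tablet stop on Day 30. For patients on one tablet, "those patients will take half a tablet (400 mg ESL or placebo) from Day 31 to Day 37".

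**Slots and Endpoint.** SAP Table 3 fills the V2 slot with "Closest non missing assessment to target day between study day 2 and 31" and the V3 slot with "Closest non missing assessment to target day between study day 32 and 71". SAP section 4.8 says: "The endpoint for a safety variable is defined as the last non-missing value collected after first intake of IMP", provided that it is not a baseline value.

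**The concern.** The effect of ESL on laboratory parameters is a stated safety objective, and the listed parameters are safety endpoints (SAP sections 2.1.3 and 2.2.3). These three tables are the only planned laboratory outputs with means and changes from baseline. A programmer who follows the text literally would leave out the one scheduled sample taken while every patient dosed as planned is on the full regimen. A between-arm difference in means that stays mostly inside the normal ranges during treatment, and is smaller after it, would then not be visible by visit. Sodium and eGFR are of particular interest, because section 5.6.2 singles out sodium for monitoring and section 2.5 ties the dose to eGFR.

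The omission does not look deliberate. The NIHSS summary (section 5.5.2.6) lists V2, the vital-signs summary (section 5.6.3) covers every slot with assessments, and section 8 records no decision to drop V2 from the laboratory tables. V1 is also not a label in SAP Table 2 or Table 3, which have V1a and V1b. Next to baseline, which for laboratory variables is the last value before first intake and so normally the V1a value, a V1 column would be close to a duplicate.

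**Working it through.** The plan gives no figure to reproduce here. The check is a count of days against the dosing period.

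Inputs:
- Day 1 is the day of first IMP intake (SAP section 4.6).
- Full regimen: Days 1 to 30. Taper: Days 31 to 37, one-tablet patients only (SAP section 2.5).
- V2: Day 8 ± 2, so Days 6 to 10 (SAP Table 2 and both schedules).
- V3: Day 38 + 4, so Days 38 to 42 (SAP Table 2; second part of the protocol schedule). It is also given as Day 38 ± 4, so Days 34 to 42 (first part of the protocol schedule; SAP section 1).
- Slots: V2 is Days 2 to 31 and V3 is Days 32 to 71 (SAP Table 3).

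Formulas: days in a window = last − first + 1. Full-regimen days are those in the window up to Day 30. Taper days are those from Day 31 to Day 37.

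| Window | Days | Full regimen | Taper (one-tablet) | Off drug, one-tablet | Off drug, half-tablet |
|---|---|---|---|---|---|
| V2 visit, Days 6–10 | 5 | 5 | 0 | 0 | 0 |
| V2 slot, Days 2–31 | 30 | 29 | 1 | 0 | 1 |
| V3 visit as 38 + 4, Days 38–42 | 5 | 0 | 0 | 5 | 5 |
| V3 visit as 38 ± 4, Days 34–42 | 9 | 0 | 4 | 5 | 9 |
| V3 slot, Days 32–71 | 40 | 0 | 6 | 34 | 40 |

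Gap from last planned dose to the V3 target day: 38 − 37 = 1 day for one-tablet patients and 38 − 30 = 8 days for half-tablet patients.

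Three readings follow.

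1. All 5 days of the V2 window lie on the full regimen. Under either V3 window, and across the whole V3 slot, the number of full-regimen days is 0.
2. For a patient who attends V3, Endpoint is normally the V3 value again, unless there is a later unscheduled sample. Endpoint therefore does not stand in for V2 in most completers of the treatment phase.
3. A laboratory sample taken on Day 1 after the first dose is slotted to V2 (SAP section 4.5), so it would also drop out of the by-visit summary.

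**The case against.** **On-drug data appear elsewhere.** The abnormality tables (15.3.2.2.1 to 15.3.2.2.3) are by visit slot with no stated restriction, so V2 is not excluded. The worst-post-baseline shift tables (15.3.2.4.1 to 15.3.2.4.3) take in any V2 value. Sodium has its own table by visit (15.3.2.6), and section 5.6.2 also classifies patients by minimum post-baseline sodium and flags any fall from baseline of more than 10 mEq/L, which is a measure of change. All results are listed. This stands: the gap is limited to means and mean changes. It does not close that gap, because these outputs give categories or individual values.

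**The listed columns can hold on-drug values.** A reader might infer that mean laboratory changes are shown only after treatment has ended. The documents do not support that. EDV bloods are taken only if EDV comes before V3. Endpoint can be a V2, EDV or unscheduled value for a patient with no V3 sample. The V3 slot opens on Day 32, while one-tablet patients are still tapering. Nor is V2 the only scheduled visit with patients on drug, since the first dose is given at V1b. It is the only scheduled post-baseline laboratory visit during full dosing.

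**It may be a slip.** V1 may be a typing error for V2, and the table shells, which are separate attachments, may already include V2. Neither can be confirmed from the protocol and SAP. If it is a slip, the text still needs correcting.

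**The harm is not shown.** The documents give no recovery times for sodium, liver enzymes or eGFR, and V3 is targeted only 1 day after the last planned dose for one-tablet patients. It cannot be said that a shift would have reversed by V3, only that the tables as written would not show the full-dose mean.

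**Conclusion.** The point holds as an omission in the text of section 5.6.2. Of the one scheduled post-baseline laboratory visit during full dosing, none is listed in the three tables that report means and changes from baseline, and this applies to every haematology, biochemistry and coagulation parameter. Nothing else in the protocol or SAP restores V2 to these tables.

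The size is modest. The tables are descriptive, with no test or decision rule attached, and the primary analysis is untouched. It would go too far to infer that on-treatment laboratory data are lost, or that a laboratory signal will be missed.

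The conclusion assumes dosing and visits as planned. A patient who stopped IMP before V2 would be off drug there too. It concerns the SAP text; whether the final output omits V2 depends on shells that are not part of the document.

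**What to change.** 1. Add V2, with value and absolute change from baseline, to Tables 15.3.2.1.1, 15.3.2.1.2 and 15.3.2.1.3.
2. Replace V1 with a defined label: V1a if the screening value was meant, or V2 if it is a slip, in which case this change also achieves item 1. Align the shells.
3. Do not label all V3 and Endpoint values as after end of treatment. That would misdescribe V3-slot values from Days 32 to 37 in one-tablet patients, and Endpoint values taken on drug. A footnote with the V3 slot range and the Endpoint definition is enough; SAP section 4.2 already asks for baseline and endpoint definitions as footnotes.
4. Reconcile the V3 window between the two parts of the protocol schedule, and between SAP section 1 and SAP Table 2. The two forms differ on whether V3 may fall in the taper.

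The cost is one extra column in three descriptive tables, with small edits to text and shells. The samples are already scheduled and the V2 slot is already defined. The change is best made before unblinding. If made later, it should be reported as a later addition.

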**Table 15.3.2.6 Signs of Hyponatraemia – Safety Set**

Number and frequency of patients will be presented by sodium level categories and by visit. This table will be provided by treatment group and in total. Visit Slots will be used.

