#### **4.5 Visit Slotting**

Due to COVID-19 pandemic visits might be delayed. Therefore, visit slots will be used for the analysis of efficacy (where applicable) and safety variables (where applicable). For a visit slot the closest non-missing assessment in time (scheduled or unscheduled) to the target day will be used (see Table 3).

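### Hyponatraemia is defined by each patient's lowest post-baseline sodium and by any fall above 10 mEq/L, but its only table reports slotted values by visit and counts neither

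*SAP*

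**What the plan says.** SAP section 5.6.2 gives sodium its own monitoring rule: "Patients will be classified by their minimum post-baseline sodium level according to the following categories". The categories are at least 135, 130 to below 135, 125 to below 130, and below 125 mEq/L. The same rule continues "and for any decrease from baseline" of more than 10 mEq/L. Both criteria describe a patient over the whole post-baseline period.

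On sampling, section 5.6.2 says that laboratory values "are collected at V1a, V2, V3, EDV (if EDV performed before V3) and, if applicable, UNS for each laboratory parameter".

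The output is Table 15.3.2.6, Signs of Hyponatraemia, in the safety set. Its description reads: "Number and frequency of patients will be presented by sodium level categories and by visit". It goes on: "This table will be provided by treatment group and in total. Visit Slots will be used".

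Section 4.5 defines the slots: "For a visit slot the closest non-missing assessment in time (scheduled or unscheduled) to the target day will be used". In Table 3 of the SAP, V2 has target Day 8 and is described as "Closest non missing assessment to target day between study day 2 and 31". V3 has target Day 38 and is described as "Closest non missing assessment to target day between study day 32 and 71".

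**The concern.** The rule and the table answer different questions. The rule asks how low each patient's sodium ever went and whether it ever fell by more than 10 mEq/L. The table asks how many patients were in each category at each visit slot, with one value per patient per slot chosen by its distance from the target day and not by its level.

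Sodium is the only analyte in section 5.6.2 with its own categories, its own table and its own listing, so a reader of the report will look to Table 15.3.2.6 for the comparison between arms. As described, that table cannot say how many patients per arm reached each minimum category. It does not mention the 10 mEq/L fall at all.

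**Working it through.** The SAP states no figure to reproduce here. The check is to apply the table's rules and compare the result with the definition.

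**1. One patient (sodium values assumed).** Baseline 140 mEq/L; Day 8 = 136; unscheduled sample on Day 18 = 122; Day 38 = 137.

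- V2 slot (Days 2–31, target Day 8). Distances from target: |8 − 8| = 0 and |18 − 8| = 10. The Day 8 value of 136 is kept and the 122 is dropped.
- V3 slot (Days 32–71, target Day 38). Distance |38 − 38| = 0. The value of 137 is kept.

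| | Sodium | Category | Fall from baseline |
|---|---|---|---|
| Table 15.3.2.6, V2 | 136 | ≥ 135 | 140 − 136 = 4 |
| Table 15.3.2.6, V3 | 137 | ≥ 135 | 140 − 137 = 3 |
| Definition in 5.6.2 | min(136, 122, 137) = 122 | < 125 | 140 − 122 = 18, above 10 |

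The definition puts this patient in the lowest category and flags the fall. The table shows the highest category twice.

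**2. No unscheduled samples.** Let a patients be below 130 at V2 and b at V3. If the smaller group lies wholly inside the larger, the number ever below 130 is max(a, b). If the groups do not overlap, it is a + b. The by-visit rows do not say which applies.

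**3. Illustration of possible size (every input assumed).** Baseline mean 139, SD 3; mean fall 2 at V2 and 1 at V3; noise SD 3 on each post-baseline value; V2 sample always taken on Day 8; an unscheduled sample during Days 2–31 in 0%, 10% or 30% of patients, with mean fall 4 or 8.

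| Unscheduled sample | Mean fall in it | Ever < 130 | V2 row < 130 | V3 row < 130 | Fall > 10, all values | Fall > 10, slotted values |
|---|---|---|---|---|---|---|
| 0% | none taken | 7.0% | 4.9% | 2.9% | 0.5% | 0.5% |
| 10% | 4 | 7.9% | 4.9% | 3.0% | 0.8% | 0.5% |
| 10% | 8 | 10.4% | 4.9% | 2.9% | 3.0% | 0.5% |
| 30% | 4 | 9.8% | 5.0% | 3.0% | 1.2% | 0.5% |
| 30% | 8 | 17.6% | 4.9% | 3.0% | 8.0% | 0.5% |

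The first row agrees with step 2: 7.0% lies between 4.9% and 4.9% + 2.9% = 7.8%. The lower rows depend on the assumption that unscheduled samples are lower than scheduled ones. They show the mechanism and do not forecast this trial.

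**4. Other outputs in section 5.6.2.**

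- Table 15.3.2.4.2 shifts biochemistry to the worst post-baseline value, but by normal range and clinical significance. It uses neither the four cut-offs nor the fall. The SAP does not say which direction is worst for an analyte that can be low or high.
- Table 15.3.2.1.2 gives change from baseline with default statistics, which include the minimum (section 4.1). That shows the largest fall in an arm at a tabulated time point, not how many patients fell by more than 10. Its listed time points do not name V2.
- Listing 16.2.4.3.6 lists patients with signs of hyponatraemia by treatment group, without counts or percentages.

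**The case against.** The case against giving this weight has several sound parts.

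- Low values do not vanish. The shift table uses the worst value by arm and is not described as slotted. Because it also uses clinical significance, a sodium of 121 judged significant and one of 134 judged not significant would fall in different cells. The listings should show the affected patients.
- Slotting is neutral between scheduled and unscheduled samples. An unscheduled value is kept when it is closer to the target day or when the scheduled one is missing. A low value is lost only if its slot holds another value closer to target.
- EDV has its own label in the slotting table, so a low sodium at an early discontinuation visit does not compete with V2.
- By-visit percentages are a legitimate summary of prevalence at a visit.
- The table shells are separate attachments and are not available here. They may contain a minimum row.

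All of this limits the point, but none of it supplies the missing counts. Clinical significance is an investigator's judgement and does not reproduce the SAP's cut-offs. The shells cannot be checked, but the wording does not point to such a row: the two urinalysis tables in the same section add to their by-visit summary a count of patients with any clinically significant abnormality, and Table 15.3.2.6 has no comparable sentence.

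A reader might also infer that sodium has recovered by V3, so that a missed on-treatment low is gone for good. The documents say nothing about recovery. Patients on a full tablet take half a tablet on Days 31 to 37, and V3 is targeted at Day 38.

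**Conclusion.** The point holds as an inconsistency between a definition and its output. Table 15.3.2.6 as described does not produce the per-patient classification in section 5.6.2, can leave out a patient's lowest sodium, and has no row for falls above 10 mEq/L. No other described output gives those counts by arm, so the incidence of hyponatraemia on the SAP's own cut-offs can be understated.

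The amount cannot be estimated: the documents do not say how many patients have more than one sodium in a slot, or how low those values are. The conclusion rests on the SAP text, with the shells unseen.

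Three stronger readings are not supported. The by-arm incidence is not shown to be biased towards zero: by-visit prevalence is a different quantity from per-patient incidence, and a dropped value may lie in the same category as the kept one. The 10 mEq/L criterion is not lost altogether: it is absent from the described tables but may appear in the listing. Hyponatraemia is also not a named endpoint: it is a derived classification under the safety endpoint of laboratory parameters.

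**What to change.** In Table 15.3.2.6 add, by treatment group and in total:

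1. Number and percentage of patients in each category of minimum post-baseline sodium, using all scheduled, unscheduled and EDV values without slotting.
2. Number and percentage of patients with any post-baseline decrease from baseline above 10 mEq/L, on the same values.

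Keep the by-visit slotted rows as supplementary. State the denominator of the new rows in the footnote, as section 4.1 already requires. The cost is a sentence in the SAP, a matching change to the table shell and a few extra rows. All the sodium values are already collected.
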